#### **7.4.3. Safety Criteria for Adjustment or Stopping Doses**

##### **Dose Modification in Potential Hy's Law Cases**

Dosing with IP for study participants meeting potential Hy's Law criteria (described in Section 12.2.7) should be interrupted until drug-induced living injury (DILI) is ruled out. Participants should be treated accordingly if hepatic laboratory elevations are due to other causes (eg, viral hepatitis, alcohol ingestion, congestive heart failure). If DILI is not ruled out, IP should be permanently discontinued; if DILI is ruled out and upon liver biochemistry returning to normal or baseline levels, dosing with IP may resume, if clinically appropriate and with agreement from the sponsor.

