#### **12.2.7. Assessment of Liver Biochemistry for Hy's Law Screening, or Hy's Law Laboratory Criteria**

Hy's Law is a principle outlining specific criteria to indicate when an individual is at high risk of a severe drug-induced liver injury (DILI) as a result of incurring hepatocellular injury sufficient to impair bilirubin excretion.

Potential Hy's Law is defined as an elevated alanine aminotransferase (ALT) and/or aspartate aminotransferase (AST)  $>3\times$  upper limit of normal (ULN) and an elevated total bilirubin  $\geq 2\times$  ULN with alkaline phosphatase  $<2\times$  ULN at any time during the study. Hy's Law criteria are met if there is no alternative explanation for the elevations in liver biochemistry other than DILI caused by the IP. The elevations of transaminases and bilirubin may occur together or at different time points during the study, therefore, to identify cases of potential Hy's Law, a comprehensive review of liver biochemistry must be performed.

The investigator is responsible for determining whether a participant meets potential Hy's Law criteria at any point during the study. If a participant has elevations in liver biochemistry, further evaluation may be required and, if elevations meet the potential Hy's Law criteria, it must be reported as an SAE within 24 hours of Investigator awareness (see Section 12.2.6 for procedure on reporting an SAE). All results of laboratory tests including alkaline phosphatase testing should also be appended to the SAE form. The investigator must continue to follow the participant until liver biochemistry returns to normal or baseline levels, or for as long as clinically indicated. In addition, the investigator should perform any necessary diagnostic evaluations to investigate the etiology of the event and update the SAE report accordingly.

These events must also be recorded as an SAE in the eCRF with the investigator's assessment of seriousness, severity, and causality, and a detailed narrative must be provided on the SAE form.

The investigator is responsible for recording data pertaining to potential Hy's Law/Hy's Law cases and for reporting AEs and SAEs in line with standard safety reporting procedures (see Section 12.2.5 and Section 12.2.6).

IP dose modifications for participants who meet potential Hy's Law criteria should be made according to Section 7.4.

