#### 8.4.2. Clinical Laboratory

Clinical laboratory assessments will include blood samples for hematology, clinical chemistry, coagulation, and urinalysis. Samples will be collected  $\leq 2$  hours prior to dosing on dosing days. On non-dosing days, collection may occur at anytime.

Any lab results considered clinically significant by the investigator will be captured as adverse events, hence will show up in AE displays.

All laboratory values will be summarized for the Safety Set using actual treatment received. Results of continuous hematology, clinical chemistry parameters, coagulation, and urinalysis parameters (quantitative) at each scheduled visit and mean changes from baseline will be summarized using standard international (SI) units. In addition, it will also include the summary of last post-baseline values on treatment (on or after first dose, on or before last dose) and on study (on or after first dose, on or before last day of the study).

All laboratory results will be listed in individual participant data listings.

Normal ranges for each parameter will be provided by the laboratory. Shift from baseline to worst post-baseline values in abnormality of results at anytime on treatment, the last value on treatment (on or after first dose, on or before last dose and the last value on study (on or after first dose, on or before last day of the study) in abnormality of results will be summarized. If a participant has both low and high post-baseline records, the participant will be counted twice for each low and high cell.

The number and percentage of participants with potentially clinically significant (PCS) values will be provided in separate displays in hematology, clinical chemistry and liver function tests provided for such occurrence for anytime on treatment, last value on treatment, within 28 Days after the last dose of treatment (follow-up period). PCS values will be identified for specific laboratory parameters as outlined in the table below.

Liver function tests will be monitored closely for PCS values, and will be summarized for occurrence anytime post-baseline for the following parameters for these PCS threshold (for condition involving more than one parameter, the results need to be from the same timepoint):

- Alanine Aminotransferase:  $>3\times\text{ULN}$ ,  $>5\times\text{ULN}$ ,  $>10\times\text{ULN}$
- Aspartate Aminotransferase:  $>3\times\text{ULN}$ ,  $>5\times\text{ULN}$ ,  $>10\times\text{ULN}$

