- Alanine Aminotransferase or Aspartate Aminotransferase:  $>3\times\text{ULN}$ ,  $>5\times\text{ULN}$ ,  $>10\times\text{ULN}$
- Alkaline Phosphatase:  $>1.5\times\text{ULN}$ ,  $>2\times\text{ULN}$
- Total Bilirubin:  $>1.5\times\text{ULN}$ ,  $>2\times\text{ULN}$
- Total Bilirubin  $>2\times\text{ULN}$  AND (Alanine Aminotransferase or Aspartate Aminotransferase  $>3\times\text{ULN}$ ) [any time post-baseline, does not need to be measured at the same time point of assessment]

- Total Bilirubin  $>2 \times \text{ULN}$  AND Alkaline Phosphatase  $<2 \times \text{ULN}$  (any time post-baseline, measured at the same time point of assessment)] AND [(ALT or AST  $>3 \times \text{ULN}$ ) AND Alkaline Phosphatase  $<2 \times \text{ULN}$ , any time post-baseline, measured at the same time point of assessment]

*Note:* The conditions in the first pair of brackets do not need to occur at the same timepoint as the conditions in the second pair of brackets.

Any lab results considered clinically significant by the investigator will be captured as adverse events, hence will show up in AE displays.

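### No composite liver row in SAP 8.4.2 matches the protocol's potential Hy's Law definition, and the section contradicts itself on whether the results must share a timepoint

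*SAP*

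**What the plan says.** Protocol 12.2.7 sets the potential Hy's Law criteria as ALT and/or AST above 3×ULN together with "elevated total bilirubin $\geq 2\times$ ULN with alkaline phosphatase $<2\times$ ULN at any time during the study". On timing it adds: "The elevations of transaminases and bilirubin may occur together or at different time points during the study". A participant who meets the criteria has a reportable event ("it must be reported as an SAE within 24 hours of Investigator awareness"), and Protocol 7.4.3 calls for dosing to be interrupted while drug-induced liver injury is investigated.

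SAP 8.4.2 lists the liver thresholds to be summarised for any post-baseline occurrence. The introductory sentence carries a general condition in parentheses: "for condition involving more than one parameter, the results need to be from the same timepoint". Two rows below it join bilirubin to the transaminases:

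- Row 1: bilirubin >2×ULN and ALT or AST >3×ULN. Its own text says that this "does not need to be measured at the same time point of assessment".
- Row 2: "Total Bilirubin $>2 \times \text{ULN}$ AND Alkaline Phosphatase" <2×ULN at one time point, and ALT or AST >3×ULN with ALP <2×ULN at one time point. A Note says that the two bracketed pairs may fall at different timepoints.

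The legible text of SAP 6.1, which lists modifications from the protocol, mentions no change to the liver criteria.

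**The concern.** There are two separate defects. The protocol's bilirubin limit includes 2×ULN and both SAP composite rows exclude it, so no SAP row reproduces the definition on which sites must act. The SAP also states a general timing rule and then contradicts it in the rows to which that rule most naturally applies.

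The composite rows are the only place where the SAP tabulates bilirubin and transaminases jointly. Few participants, if any, would be expected to meet such criteria, so a single case can change what the row appears to say. If an investigator reports a potential Hy's Law SAE and the composite row does not count that participant, two displays in the same report disagree and the plan provides no reconciliation.

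**Working it through.** The documents give no figure to reproduce, so the check is logical. The inputs are the criteria in Protocol 12.2.7 and the introductory sentence, Row 1, Row 2 and the Note in SAP 8.4.2. With all values in multiples of ULN:

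- Protocol: ALT/AST >3 at some visit and bilirubin ≥2 at some visit, with ALP <2.
- Row 1, by its own text: bilirubin >2 at some visit and ALT/AST >3 at some visit.
- Row 2, by its own text and Note: (bilirubin >2 and ALP <2 at one visit) and (ALT/AST >3 and ALP <2 at one visit).
- Either row with the introductory sentence taken literally: all of its conditions at a single visit.

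These rules were applied to five hypothetical participants. ALT is 4 and ALP is 1 at each elevation unless stated.

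| Profile | Protocol case | Row 1, own text | Row 1, literal lead-in | Row 2, own text | Row 2, literal lead-in |
|---|---|---|---|---|---|
| A: bilirubin 2.5, same visit as ALT | yes | yes | yes | yes | yes |
| B: bilirubin exactly 2.0, same visit | yes | no | no | no | no |
| C: bilirubin 2.5, different visit | yes | yes | no | yes | no |
| D: bilirubin exactly 2.0, different visit | yes | no | no | no | no |
| E: as C, ALP 2.2 at the bilirubin visit | unclear | yes | no | no | no |

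Among the four clear protocol cases (A to D), Row 2 counts A and C under its own text (2 of 4) and only A under the literal lead-in (1 of 4). With bilirubin ≥2 and Row 2's own timing it counts all four. These fractions describe chosen profiles and are not rates.

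B and D isolate the threshold: they are missed under either timing reading, solely because bilirubin equals 2×ULN. C isolates the timing conflict: it is lost only if the introductory sentence prevails. E shows a third gap. The protocol does not say when ALP <2×ULN must hold, so whether E is a protocol case cannot be settled from the text.

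B and D remain visible elsewhere in the same display: ALT 4 exceeds 3×ULN, and bilirubin 2.0 exceeds the 1.5×ULN limit of the lower single-parameter bilirubin row.

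Separated elevations are plausible on the schedule. Protocol Table 2 places laboratory draws at Screening and Days 1, 28, 84 and 112. On dosing days samples precede the dose, so Day 1 is baseline and the scheduled post-baseline draws are Days 28, 84 and 112. The gaps are 84 − 28 = 56 days and 112 − 84 = 28 days.

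**The case against.** The strongest reply is that specific text governs general text. Row 1 states its timing outright. Row 2 states which pairs must coincide, and the Note frees the two pairs from each other. Inside each bracket Row 2 even agrees with the introductory sentence. A programmer would have to disregard the row being programmed in order to lose profile C. That largely stands: the row text would normally prevail, and a reader who infers that every case with separated elevations will be dropped goes further than the documents allow. What remains is a stated rule that is untrue of Row 1 and of Row 2 across its brackets.

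A reader might also infer that a reported case could disappear from the liver display, or that the SAP never looks below a strict 2×ULN for bilirubin. Neither is supported. There is a 1.5×ULN bilirubin row, all laboratory results are listed by participant, serious TEAEs are tabulated, and so are TEAEs leading to interruption of IP.

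The threshold gap affects only results exactly equal to 2×ULN. The documents give neither the bilirubin ULN nor the reporting precision, so how often that would occur cannot be derived from them. Protocol 12.2.7 also requires continued follow-up of an elevation, so results between scheduled visits can be expected, and these may narrow the gap between the two peaks.

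Finally, the SAP does not label these rows Hy's Law, and the protocol criterion is an investigator's reporting trigger, so exact agreement is promised nowhere. That is fair. Even so, the rows use the same three analytes at nearly the same limits and will be read as the protocol's definition, so an unexplained difference invites misreading.

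**Conclusion.** The point holds as a limited inconsistency. Certain from the text: no composite row in SAP 8.4.2 uses the protocol's bilirubin criterion, the legible text of SAP 6.1 does not declare the difference, and the same-timepoint sentence conflicts with Row 1 and with the Note to Row 2. Conditional: a participant with bilirubin exactly at 2×ULN is missing from the composite rows under any reading, and one with separated elevations is missing only if the introductory sentence is applied literally.

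The effect is confined to safety reporting: the composite count may fall short of the number of potential Hy's Law SAEs. The expected number of cases is not given in the documents; that it is small is an assumption. The primary analysis, power and type I error are untouched. This is a minor correction, worth making because it is cheap and because one case can matter in a near-empty row.

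**What to change.** - Reconcile SAP 8.4.2 with Protocol 12.2.7 and include one composite row that uses the definition as finally reconciled. The existing rows may stay. Which bilirubin threshold is clinically right is for the sponsor to decide; the requirement here is that the two documents agree or that the SAP declares the difference in 6.1.
- Limit the same-timepoint sentence to parameters within one bracket (bilirubin with its ALP, transaminase with its ALP), as Row 2 and its Note already do, and exempt Row 1 explicitly.
- State when the ALP <2×ULN condition must hold, so that a participant like profile E is classified the same way in both documents.
- Before lock, compare the participants flagged by the reconciled row with the reported potential Hy's Law SAEs, and explain any difference. SAP 5.4 plans the lock in two parts, so repeat the comparison at Part 2 for the remaining follow-up data.

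The cost is a few lines of SAP wording, one program condition and a short listing check. No new data are needed.

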**Table 15: Potentially Clinically Significant Values for Specific Laboratory Parameters**

Laboratory Parameter	Sex	Units	Criteria for PCS Values (Observed values)	
			High	Low
Hematology				
Hemoglobin	Male	g/L	>185	<115
	Female	g/L	>170	<100
Hematocrit	Male	Fraction of 1	>0.55	<0.385
	Female	Fraction of 1	>0.49	<0.345
Platelet count		$10^9/\text{L}$	>600	<125
White blood cell		$10^9/\text{L}$	>15	<2.5
Basophils		$10^9/\text{L}$	>0.5	NA
Eosinophils		$10^9/\text{L}$	>1.5	NA
Neutrophils		$10^9/\text{L}$	NA	<1.5
Lymphocytes		$10^9/\text{L}$	>6.0	<0.5
Monocytes		$10^9/\text{L}$	>1.4	NA
Coagulation				
Prothrombin time (PT)		Sec	$\geq 1.11 \times \text{ULN}$	Not Specified
Partial thromboplastin time (PTT)		Sec	$>1.5 \times \text{ULN}$	Not Specified
Serum Chemistry				
Albumin		g/L	>70	<28

Blood urea nitrogen		mmol/L	>10.71	NA
Calcium		mmol/L	>2.75	<2.0
Chloride		mmol/L	>120	<90
Creatinine		mmol/L	>3xULN or >3x Baseline	
Gamma Glutamyl Transferase			>3xULN	
Glucose		mmol/L	>13.9	<2.8
Sodium		mmol/L	>150	<132
Potassium		mmol/L	>5.4	<3.3
Protein		g/L		<45
Bicarbonate		mmol/L	>34	<18
Phosphorus		mmol/L	>1.94	<0.61
Liver Function Tests (LFT)				
Bilirubin		µmol/L	>2xULN	NA
Aspartate Aminotransferase		U/L	>3xULN	NA
Alanine Aminotransferase		U/L	>3xULN	NA
Alkaline Phosphatase		U/L	>1.5xULN	NA

#### 8.4.3. 12-Lead Electrocardiogram

A single 12-lead ECG under Protocol Amendment 2 and triplicate 12-lead ECG under Original Protocol and Protocol Amendment 1 will be performed after the participant has been resting in the supine position for at least 5 minutes. If the multiple 12-lead ECG are performed, the average of all values on the same date will be used in the summary. If there are both scheduled visit and unscheduled visit on the same date, all the assessments on that date are considered as the scheduled visit for the summary. A summary of the observed values (raw values for the single ECG; average values for the multiple ECG on the same date) and change from baseline values will be summarized by each scheduled visit for the following ECG parameters: heart rate, PR, QRS, QT, and QTcF interval. This summary will also include the last values on treatment and on study. A by-participant listing of 12 lead ECG will also be provided for each of the ECG measurements.

Each ECG is evaluated as ‘normal’, ‘abnormal, not clinically significant’ and ‘abnormal, clinically significant’. The number and percentage of participants with the categories of

‘abnormal, clinically significant’ and ‘abnormal, not clinically significant’ from the latest triplicated ECG value will be provided at baseline and each post-baseline scheduled assessment time point.

Potentially clinically significant values of QTcF as outlined in the table below will be summarized by treatment for anytime on treatment, last value on treatment, within 28 Days after the last dose of treatment (follow-up period). This analysis includes triplicate values individually and is not based on average value. Electrocardiogram findings will be listed by participant and visit.

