### 12.1.6. Electrocardiogram

A 12-lead ECG will be performed at the time points described in [Table 2](#). At each time point, a single ECG will be recorded. The standard intervals (heart rate, PR, QRS, QT, and QT corrected according to Fridericia's formula [QTcF]) as well as any rhythm abnormalities will be recorded.

Electrocardiograms will be performed after the participant has been resting in a supine position for at least 5 minutes. When ECG measurements coincide with safety assessments, vital signs assessment or blood draws, blood draws should be carried out after ECG and vital signs.

All abnormal ECGs will be interpreted by an investigator as CS or NCS in source documents.

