**Table 16. Potentially Clinically Significant Values for 12-Lead ECG Parameters**

12-Lead ECG	Units	Criteria for PCS Values (Observed values)		Criteria for PCSC values (Change from Baseline)	
		High	Low	Increase	Decrease
QTcF	msec	>450 but $\leq$ 480 >480 but $\leq$ 500 >500	NA	$\geq$ 30 to 60 >60	NA

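### SAP 8.4.3 counts the investigator's ECG category from the latest triplicate reading only, so an earlier clinically significant reading can be missing from the by-visit count (minor)

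*SAP*

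**What the plan says.** SAP 8.4.3 records that the number of ECGs per time point changed during the trial: "A single 12-lead ECG under Protocol Amendment 2 and triplicate 12-lead ECG under Original Protocol and Protocol Amendment 1". The current protocol has one (Protocol 12.1.6): "At each time point, a single ECG will be recorded".

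The same SAP section then gives three rules for repeated ECGs:

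- **Observed values and changes by visit.** With multiple ECGs, "the average of all values on the same date will be used in the summary". Scheduled and unscheduled ECGs on the same date are treated as the scheduled visit.
- **Investigator category.** The rating is made per ECG: "Each ECG is evaluated as ‘normal’, ‘abnormal, not clinically significant’ and ‘abnormal, clinically significant". The count and percentage in the two abnormal categories come "from the latest triplicated ECG value will be provided at baseline and each post-baseline scheduled assessment time point".
- **QTcF thresholds (Table 16).** "This analysis includes triplicate values individually and is not based on average value".

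Table 11 of the SAP marks the ECG entry for abnormality and clinical significance with an asterisk, meaning listing only. Section 8.4.3 nevertheless promises a number and percentage for it.

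**The concern.** A by-visit count of clinically significant ECGs is read as the number of participants for whom the investigator made that call at that visit. If the count keeps only the last of three ratings, a milder later rating replaces a worse earlier one taken on the same occasion. The table can then show fewer participants with a clinically significant ECG than the listing behind it.

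The rule also differs from the SAP's own practice. Laboratory shifts are shown to the worst post-baseline value (8.4.2, alongside last-value displays). Adverse events are counted once per participant at maximum severity and at the strongest relationship to treatment (8.4.1). In the ECG category display, a less severe later rating prevails and no worst-case display stands beside it.

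At stake is the completeness of one descriptive safety table and its agreement with the listing.

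**Working it through.** The plan states no figure for this point, so there is none to reproduce. The check has four steps.

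**1. Who is affected.** Only participants with three ECGs at a time point, that is, those under the Original Protocol or Amendment 1. With a single ECG, the latest rating is the only rating. The documents do not say how many participants had triplicates.

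**2. How often the latest-reading rule misses a clinically significant rating.** Assume that k of the three readings are so rated and that their positions are random. The rating is missed when the third reading is not among the k, so P(missed) = (3 − k)/3.

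| k of 3 rated clinically significant | Missed, latest reading | Missed, worst category |
|---|---|---|
| 1 | 2/3 | 0 |
| 2 | 1/3 | 0 |
| 3 | 0 | 0 |

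These are conditional on disagreement within a triplicate. The documents do not say how often that occurs, so no trial-level count can be derived.

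**3. What a worst-category rule costs in comparability.** A triplicate participant has three chances per visit to be rated abnormal, against one for a later participant. Over the two scheduled on-treatment ECG visits, Day 28 and Day 84 (SAP Table 13 and Appendix A), that is 6 readings against 2. If the chance per reading is p and readings are independent, the chance per visit is 1 − (1 − p)³:

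- p = 1%: 1 − 0.99³ = 2.97%
- p = 5%: 1 − 0.95³ = 14.3%

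Both values of p are assumptions. Positive correlation between readings taken together would bring these figures down towards p. Randomization is 1:1 in blocks of 4 (SAP 5.3), so triplicate participants should be similarly frequent in both arms.

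**4. Whether the QTcF threshold rule should change too.** Take one participant with an assumed true QTcF of 440 ms, independent readings, and within-visit SD of 8 ms (range 5 to 12). The chance per visit of exceeding 450 ms is p = 1 − Φ(10/SD) for one reading, 1 − (1 − p)³ for any of three, and 1 − Φ(10√3/SD) for the mean of three.

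| SD (ms) | Any of three | Single | Mean of three |
|---|---|---|---|
| 5 | 6.7% | 2.3% | under 0.1% |
| 8 | 28.5% | 10.6% | 1.5% |
| 12 | 49% | 20% | 7% |

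At SD 8, counting individual readings gives triplicate participants 28.5/10.6 = 2.7 times the single-ECG rate. Using the mean gives them 1.5%, and the ratio reverses to 10.6/1.5, about 7. The mean narrows the absolute gap but does not make the protocol versions comparable.

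This example is a person 10 ms below the limit. A simulated population gives smaller differences. It assumes mean 410 ms, between-participant SD 15, visit-to-visit SD 8, replicate SD 3 to 10, and two on-treatment visits. The share with any on-treatment value above 450 ms is 2.4% to 7.5% counting each reading, 1.7% to 3.8% with single ECGs, and 1.6% to 2.2% with the mean of three.

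**The case against.** **Nothing is lost from reporting.** This largely stands. SAP 8.4.3 provides a listing of each ECG measurement. Protocol 12.2.1 makes an ECG change an adverse event if the investigator considers it clinically significant, with an exception for changes clearly attributable to another adverse event. A reader might infer that the plan lets a clinically significant ECG disappear; the documents do not support that. What can be incomplete is the by-visit category count.

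**The wording may mean the latest triplicate set, not the latest reading.** This is possible, because the section does pool ECGs taken on one date. The singular noun and the per-ECG rating favour the narrower reading. If the set was meant, the plan gives no rule for choosing a category when the three ratings differ, so the sentence still needs repair.

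**The QTcF thresholds have a similar fault.** A reader might infer that counting each reading wrongly inflates the QTcF table and that the daily mean should replace it. It is true that any of three readings can only equal or exceed a single reading or the mean for the period at any time on treatment. But the rule is explicit and pre-specified, and it is a defensible sensitive screen. Averages are already in the by-visit summary. Under the mean, one extreme reading could leave the table, and step 4 shows that the versions would still not be comparable.

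**A worst-category rule also gives early participants more chances.** This stands as a small cost. It raises absolute rates for triplicate participants but does not systematically favour an arm.

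**The impact is small.** This stands. SAP 8.4 plans no hypothesis tests on safety, and the named safety endpoint is the proportion with treatment-emergent adverse events.

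**Conclusion.** The concern holds for the investigator category only, and it is minor. On the natural reading of SAP 8.4.3, an abnormal, clinically significant first or second reading is left out of the by-visit count when the last of the three is not so rated. That happens 2 times in 3 if exactly one reading is so rated and 1 time in 3 if two are, assuming random order. The overall number affected cannot be derived, because neither the number of triplicate participants nor the rate of disagreement within triplicates is given.

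The documents do not support a claim of bias between arms or of any effect on the efficacy conclusions. The mismatch between Table 11 (listing only) and 8.4.3 (number and percentage) is an inconsistency in the text and needs settling in either case.

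**What to change.** 1. In SAP 8.4.3, replace the latest-reading rule: at baseline and at each scheduled post-baseline time point, count each participant once, under the worst investigator category among all ECGs on that visit date (clinically significant above not clinically significant above normal). This covers single ECGs as well and settles which reading is meant.
2. Amend the ECG entry in Table 11 so that it agrees with the summary that 8.4.3 promises.
3. Footnote the table: participants under the Original Protocol and Amendment 1 have up to three ratings per visit and later participants one, with the number of each by arm.
4. Leave the QTcF threshold count of individual readings as it is. A display based on the mean for the date may be added as supplementary.

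The cost is one revised sentence, one table cell, one footnote and a small programming change from last to worst. The downside is the unequal number of chances per visit shown in step 3, which the footnote discloses and which randomization should balance between arms.
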